## 6.9 PERIPHERAL BLOOD IMMUNOGENICITY ASSESSMENTS

Whole blood and serum samples will be obtained at baseline (screening and Day 0 prior to dosing) and at Weeks 15, 27, 48, 74 and 96. Details of the immunology sample collection and shipment information will be provided in the Laboratory Manual.

A standardized binding ELISA may be performed to measure the anti-HPV-16/18 antibody response induced by VGX-3100.

PBMCs will be isolated from whole blood samples. Assessment of cellular immune activity may occur via the application of the Interferon- $\gamma$  enzyme-linked immunosorbent spot (IFN- $\gamma$  ELISpot) assay as well as flow cytometry.

Additional assessment of cellular immune activity may occur via the application Flow Cytometry for the purposes of performing a Lytic Granule Loading Assay. The Lytic Granule Loading assay may examine the following external cellular markers: CD3, CD4, CD8 (T cell identification), CD137, CD38 and CD69 (T cell activation markers) as well as PD-1 (exhaustion/activation marker). The Lytic Granule Loading assay may additionally analyze the following intracellular markers: Granzyme A, Granzyme B, Granzyme C and Perforin (proteins involved in lytic degranulation and cytotoxic potential). Markers examined in this assay may change as new relevant data become available.

## 6.10 TISSUE IMMUNOGENICITY ASSESSMENT

If there is residual tissue or additional slides in the paraffin block after histologic diagnoses have been rendered, then unstained slides and/or the relevant paraffin blocks may be collected for immunohistochemistry (IHC). Assessment of markers may include, but are not limited to, CD8+ and FoxP3+ infiltrating cells as well as assessment of cell death via Cleaved Caspase 3 assessment. Additional assessments may include visualization of Granzyme B, Perforin, CD137, CD103 and PD-L1 in cervical tissue as sample allows. Markers listed here may change as new relevant information becomes available.

## 6.11 HLA TYPING

HLA testing will be performed on PBMC from a single blood sample collected for immunogenicity analysis if available.

The DNA extracted from the blood sample will be used to determine if alleles at the MHC locus affect the immune response to study treatment. Data arising from this study will be subject to same confidentiality as the rest of the study. This specimen will be destroyed immediately after the analysis and the results checked.

## 6.12 VULVAR HPV TESTING

A 4 mm vulvar punch biopsy sample will be obtained at Screening, Weeks 48, 74, and 96, and will be sent to a central laboratory for HPV genotyping by PCR. In the case of multifocal disease, a 4 mm vulvar biopsy will be obtained from two regions of most advanced and severe disease as judged by the investigator. The subject will be requested to abstain from sexual activity and refrain from use of douching vulvar biopsy samples to eliminate potential interference with the results of HPV testing.

## 6.13 COLPOSCOPY, PAP SMEARS AND HPV TESTING

Cervical colposcopy will be performed at Screening and at Week 96 for all subjects. Photographs of the cervix should be obtained if lesions are identified.

Pap smears will be obtained using ThinPrep™ test kits at Screening, Weeks 27, 48, 74 and 96, and read in a central laboratory. HPV PCR will be performed on the ThinPrep™ specimen. At each of these visits, menstrual cycle status & recent history will be collected via self-report. If the Pap smear result suggests progression to cancer the investigator may schedule an ad hoc visit to perform a colposcopy and possible biopsy if clinically indicated.

The subject will be requested to abstain from sexual activity and refrain from use of douching or vaginal lubricants/medication for a period of 24 hours prior to collection of ThinPrep™ samples to eliminate potential interference with the results of HPV testing.

## 6.14 VULVOSCOPY, PHOTOGRAPHS, AND BIOPSIES

Eligible subjects are enrolled in the study based on the diagnosis of vulvar HSIL confirmed by the PAC. Subjects will undergo vulvoscopy to identify the lesion(s). Digital photographs of the vulva will be captured after application of acetic acid to document the clinical findings. If a biopsy or surgical excision is performed, images of the vulva should be collected before and after the procedure. Each site will be instructed on 1) the technique for capturing the proper images using a standard approach, and 2) the process for uploading the images to a secure server.

In the case of multifocal disease, the two lesions which appears to have the highest likelihood according to the investigator of most advanced disease and which is of adequate size to ensure that a visible lesion remains after punch biopsy should be chosen for vulvar biopsy and documented using photography.

Interval vulvoscopies will be performed at Day 0, Weeks 4, 12, 27, 48, 74 and 96. An unscheduled biopsy may be performed at the discretion of the investigator if there is suspicion of disease progression. Guidelines for managing the findings of unscheduled biopsies for suspected disease progression are described in [Table 13](#). Consult the Medical Monitor for any planned departures from these guidelines.

**Table 13: Guidelines for Managing Findings of Vulvar Biopsies for Suspected Disease Progression**

Vulvar Biopsy Results	Action
Vulvar HSIL	May continue study treatment/EP and visits according to protocol schedule of events
Microinvasive or Invasive Carcinoma	Discontinue study treatment/EP and proceed with excisional therapy; continue safety follow-up.

Subject safety is paramount in this study. Therefore, if at any time the investigator may suspect disease progression and the standard of medical care would be to perform an unscheduled biopsy or excision, then his or her medical judgment should prevail over the default “Schedule of Events”, [Table 1](#).

### 6.15 CONCOMITANT MEDICATIONS/TREATMENTS

All medications (prescription and nonprescription) taken within 8 weeks prior to screening biopsy date of eligible subjects must be recorded on the CRF. Actual or estimated start and stop dates must be provided. Medical procedures performed within 8 weeks prior to screening biopsy date of eligible subjects that do not affect subject’s eligibility for participation and during the study (including over the counter or herbal), will be recorded on the CRFs. This information will be obtained from the subject and abstracted from any available medical records. The indication for the medication, dose, and dose regimen will be documented. Medication that is considered necessary for the subject’s safety and well-being may be given at the discretion of the investigator and recorded in the appropriate sections of the CRF.

### 6.16 RESTRICTIONS

The following medications and treatments are prohibited:

- Previous treatment with imiquimod for vulvar HSIL within 4 weeks prior to screening
- Long term use ( $\geq 7$  days) of oral or parenteral glucocorticoids at a dose of  $\geq 20$  mg/day of prednisone equivalent (use of inhaled, nasal, otic and ophthalmic corticosteroids are allowed)
- Disease modifying doses of anti-rheumatic drugs (e.g., azathioprine, cyclophosphamide, cyclosporine, methotrexate), and biologic disease modifying drugs such as TNF- $\alpha$  inhibitors (e.g. infliximab, adalimumab or etanercept) at screening and throughout the study
- Administration of any non-study related, non-live vaccine within 2 weeks of any study treatment or within 4 weeks of any study treatment for any non-study related live vaccine
- Blood thinners/Anticoagulants within 2 weeks of any study treatment

#### 6.16.1 OTHER RESTRICTIONS

Subjects should not use alcohol or drugs that would interfere with study requirements during the course of the study and should report ALL medications/drugs taken to the investigator and/or other study personnel.

Subjects should refrain from becoming pregnant until 6 months following the last dose of investigational product by using appropriate contraceptive measures (See Inclusion Criteria, [Section 4.1](#)). Lapses in contraceptive use should be reported to investigator and/or other study personnel.

Subject should abstain from sexual activity and refrain from use of douching or vaginal lubricants/medication for a period of 24 hours prior to collection of ThinPrep™ samples.

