
1. Describe the efficacy of VGX-3100, administered alone or in combination with imiquimod, at Week 74 and/or Week 96 as measured by reduction in the surface area of vulvar lesion(s), in subjects who did not have complete lesion resolution at Week 48
	
1. Percent reduction in the cumulative surface area of the acetowhite vulvar lesion(s) as determined by the quantitative analysis of standardized photographic imaging at Week 74 and/or Week 96 compared to baseline. Results will be classified as: no clinically significant lesion resolution (reduction in lesion area of 0-25%), partial lesion area resolution (>25% and <100% reduction) and complete lesion resolution (no visible lesion).

2. Describe the efficacy of more than 4 doses of VGX-3100, alone or in combination with prior imiquimod, as measured by histologic regression of vulvar HSIL
	
2. Proportion of subjects with no evidence of vulvar HSIL on histology (i.e. biopsies or excisional treatment) at Week 74 for subjects who receive 5 doses of VGX-3100 and at Week 96 for subjects who receive 6 doses of VGX-3100

3. Describe the efficacy of more than 4 doses of VGX-3100, alone or in combination with prior imiquimod, as measured by virologic clearance of HPV-16/18
	
3. Proportion of subjects with no evidence of HPV-16/18 in vulvar tissue samples at Week 74 and/or Week 96.

4. Evaluate tissue immune responses to VGX-3100, and VGX-3100 with imiquimod, as measured in vulvar tissue samples
	
4. Assessment of CD8+ and FoxP3 infiltrating cells.

5. Describe virologic clearance of HPV-16/18 from other anatomic locations outside the vulva
	
5. Proportion of subjects who have cleared HPV-16/18 on specimens from other anatomic locations without surgical intervention (inclusive of cervix, oropharynx, vagina and intra-anus) at Week 48

 Digital photos will be analyzed with a computer program to calculate the total lesion size in cm^2.

 Additional assessments may include visualization of PD-L1, Granulysin, Perforin, CD137, CD103 and possibly other relevant markers identified in the literature in vulvar tissue as sample allows.

6. Characterize HLA haplotypes and the correlation with efficacy	6. Proportion of subjects with regression of HSIL on histology (i.e. biopsies or excisional treatment) at Week 48 visit

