- If any SAE (or potentially life-threatening AE) or death assessed as related to study treatment occurs, further enrollment and study treatment will be halted immediately until a thorough investigation has been conducted by the Medical Monitor, Principal Investigator for the trial, IRB (if applicable) and the DSMB.
- If three or more subjects in this study experience the same Grade 3 or 4 adverse event, assessed as related to study treatment, further enrollment and study treatment will be halted immediately until a thorough investigation has been conducted by the Medical Monitor, Principal Investigator for the trial, and the DSMB.
- In the event of two identical, unexpected, Grade 4 toxicities, assessed as related to study treatment, further enrollment and study treatment will be halted immediately until a thorough investigation has been conducted by the Medical Monitor, Principal Investigator for the trial, IRB (if applicable) and the DSMB.

The sponsor or designee will notify all investigators and IRBs/EC (if required) regarding the outcome of any investigation stemming from a Study Pause.

Immunogenicity Assessment: The study will explore humoral and cell mediated immune responses to VGX-3100, and VGX-3100 with imiquimod, in blood samples taken at baseline (both Screening as well as Day 0 prior to dosing) and at Weeks 15, 27, 48, 74 and 96. Vulvar samples will also be analyzed for evidence of immune responses at Screening and at Weeks 48, 74 and 96.

Virologic Assessment: Tissue samples will be obtained to characterize HPV infection at Screening, Week 48, 74 and 96. Cervical samples, oropharyngeal rinse samples, vaginal, and intra-anal tissue swab samples will be obtained to characterize HPV infection in samples from study subjects taken at Screening (cervical sample only), Day 0 prior to dosing (OP, vaginal and intra-anal only) and at Weeks 27, 48, 74, and 96.

If there is residual tissue in the paraffin block after histologic diagnoses have been rendered, then unstained slides and/or the relevant paraffin blocks will be collected for immunohistochemistry (IHC) and in situ hybridization (ISH) for the presence of HPV-16/18. Whenever possible, these studies will be performed on tissue sections from the diagnostic biopsy (pre-dose) and from tissue obtained post-dose (Week 48, 74 and 96).

HLA haplotyping: A sample from one time point during the study will be tested to explore the relationship between subject HLA haplotypes and regression.

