- b Screening vital signs must include a measured height and weight and calculated BMI (Bodyweight in kilograms divided by height in meters squared). Weight will be measured at all dosing visits.
- c Screening 12-lead ECG, complete blood count (CBC), serum electrolytes, blood urea nitrogen (BUN), creatinine (Cr), glucose, ALT, CPK and urinalysis performed within 30 days prior to first dose administration.
- d Negative spot urine pregnancy test is required at screening and prior to each study treatment, vulvoscopy and biopsy/surgical excision.
- e At least 34 mL (4 x 8.5 mL yellow (ACD) tubes) whole blood and 4 mL serum per time point. At least 68 mL whole blood and 8 mL serum should be collected prior to first dose.
- f At least 51 mL [6 x 8.5 mL yellow (ACD) tubes] whole blood and 4 mL serum should be collected at Week 27.
- g HLA testing will be performed once from an existing PBMC sample.
- h HPV genotyping and Pap smears are performed on the same ThinPrep™ cervical specimen.
- i An additional visit may be scheduled to perform vulvoscopy if worsening of disease is suspected. Biopsies should not be performed at any visit other than at entry (Screening), Week 48, and Weeks 74 and 96 for Subgroups C and D unless the investigator suspects invasive cancer. All biopsy samples and/or excision samples must be sent to the PAC for review.
- j Standardized high resolution digital imaging of the vulva and the associated acetowhite stained lesion(s) must be performed prior to and after biopsy, and at all vulvoscopy examinations. Additionally, standardized high resolution digital imaging should be obtained during examinations of the vagina if lesions are identified, for documentation.
- k Tissue specimen and slides from all excised tissue must be reviewed by the PAC and residual vulvar tissue from entry, Week 48, 74 or Week 96 specimen(s) (paraffin blocks or unstained slides) should be sent to the central pathology laboratory for immunohistochemistry (IHC) and HPV testing.
- l HPV genotyping is performed on vulvar tissue specimen using a PCR based assay.
- m Potential dosing at Week 52 and Week 78 is applicable for partial responders only.
- n Subjects will take home imiquimod plus an imiquimod dosing log to document their use of imiquimod. Administration of imiquimod begins on Day 0.

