### 3.5 VIROLOGIC ASSESSMENT

Tissue samples will be obtained to characterize HPV infection at Screening, Week 48, 74 and 96. Cervical samples, oropharyngeal (OP) rinse samples, vaginal, and intra-anal tissue swab samples will be obtained to characterize HPV infection in samples from study subjects taken at Screening (cervical sample only), Day 0 prior to dosing (OP, vaginal and intra-anal only) and at Weeks 27, 48, 74 and 96.

If there is residual tissue in the paraffin block after histologic diagnoses have been rendered, then unstained slides and/or the relevant paraffin blocks will be collected for immunohistochemistry (IHC) and in situ hybridization (ISH) for the presence of HPV-16/18. Whenever possible, these studies will be performed on tissue sections from the diagnostic biopsy (pre-dose) and from tissue obtained post-dose (Week 48, 74 and 96).

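### The 24-hour pre-sampling restriction is tied to ThinPrep visits, so the Day 0 vaginal and intra-anal baselines (and, less certainly, the oropharyngeal one) are collected under different conditions from their follow-up samples

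*Protocol*

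**What the plan says.** Section 6.16.1 of the protocol (versions 1.0 and 1.1) sets this restriction for the participant: "abstain from sexual activity and refrain from use of douching or vaginal lubricants/medication for a period of 24 hours prior to collection of ThinPrep™ samples". Section 6.13 repeats the request and gives its purpose: "for a period of 24 hours prior to collection of ThinPrep™ samples to eliminate potential interference with the results of HPV testing". It does not say whether the interference makes a result falsely positive or falsely negative.

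ThinPrep is the cervical sample. A footnote to Table 1 states that "HPV genotyping and Pap smears are performed on the same ThinPrep™ cervical specimen". Section 6.13 sets its timing: "Pap smears will be obtained using ThinPrep™ test kits at Screening, Weeks 27, 48, 74 and 96". Day 0 is not on that list.

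Section 3.5 gives this schedule for the HPV samples from outside the vulva: "Screening (cervical sample only), Day 0 prior to dosing (OP, vaginal and intra-anal only) and at Weeks 27, 48, 74 and 96".

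Exploratory endpoint 5 uses these samples at Week 48: "Proportion of subjects who have cleared HPV-16/18 on specimens from other anatomic locations without surgical intervention", covering cervix, oropharynx, vagina and anus. Section 8.9 analyses it in the same way as vulvar clearance, that is, as a proportion with a Clopper-Pearson interval.

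**The concern.** Clearance compares a sample at baseline with a sample at Week 48, so the two should be taken under the same conditions. The protocol names recent sexual activity, douching and vaginal products as possible sources of interference with HPV results. It controls them at every follow-up collection from the vagina, anus and oropharynx, because a ThinPrep is taken at the same visit. It does not control them at the one baseline collection from those sites. A change in collection conditions is therefore mixed with any true change in infection.

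At stake is how far the Week 48 clearance estimate at these sites can be trusted. Both arms receive VGX-3100 on the same schedule, and the 2% historical rate is set for the primary endpoint only. There is no comparison group against which a sampling effect at these sites could be separated from clearance.

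**Working it through.** The plan gives no figure on this point to reproduce. The check sets the schedule against the restriction, then asks what the mismatch could do to the estimate.

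**Step 1: schedule against restriction** (Table 1 and sections 3.5, 6.2 and 6.13)

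| Site | Baseline sample | Restriction at baseline | Follow-up samples | Restriction at follow-up |
|---|---|---|---|---|
| Cervix (ThinPrep) | Screening | yes | Weeks 27, 48, 74, 96 | yes |
| Vagina, anus (swabs) | Day 0 | no | Weeks 27, 48, 74, 96, with ThinPrep | yes, through the visit |
| Oropharynx (rinse) | Day 0 | no | Weeks 27, 48, 74, 96, with ThinPrep | yes, through the visit |

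Two other provisions might have covered Day 0, but neither does. The Screening window in Table 1 ends at day -1, so the request before the Screening ThinPrep does not reach Day 0. Section 6.12 makes a similar request before vulvar biopsy, without a time window, but biopsies are at Screening and Weeks 48, 74 and 96 only.

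**Step 2: possible effect on observed clearance**

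Let π be true baseline prevalence at a site, q true clearance, c the Day 0 false-positive rate and f the Day 0 false-negative rate, with follow-up taken as error-free. Then

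observed clearance = [π(1−f)q + (1−π)c] / [π(1−f) + (1−π)c].

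The protocol gives none of these values. All are assumptions, shown as ranges.

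- *False positives only at Day 0* (c = 5% to 10%, π = 20% to 60%). Example with π = 0.4, q = 0.2, c = 0.05: (0.08 + 0.03)/(0.40 + 0.03) = 25.6%. Over the range, true 20% is observed as 22.6% to 42.9%, and true 40% as 41.9% to 57.1%. The shift is upward.
- *Random false negatives only at Day 0* (f = 10% to 20%). The factor (1−f) cancels, so 20% stays 20% and 40% stays 40%. There is no bias, only fewer evaluable women.
- *Low-load infections missed at Day 0*. Suppose 30% of infections are low-load and clear at 60%, and the rest clear at 20%. True clearance is 0.3×0.6 + 0.7×0.2 = 32%. If 20% of the low-load infections are missed: (0.3×0.8×0.6 + 0.14)/(0.3×0.8 + 0.7) = 0.284/0.94 = 30.2%. If 40% are missed: 0.248/0.88 = 28.2%. The shift is downward.
- *Both mechanisms*, π = 0.4, true 32%. With c = 1% and 40% of low-load infections missed: (0.4×0.248 + 0.006)/(0.4×0.88 + 0.006) = 29.4%. With c = 2% and 40% missed: 30.5%. With c = 5% and 20% missed: (0.4×0.284 + 0.03)/(0.4×0.94 + 0.03) = 35.4%. The sign goes either way.

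**Step 3: with the restriction at both times**

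With negligible error at Day 0 as well as at follow-up (c = f = 0), the formula returns q, whichever mechanism was at work.

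**The case against.** A reader might infer that clearance outside the vulva is biased upward: recent sexual contact gives a transient positive at Day 0, abstention turns it negative at Week 48, and this is scored as clearance. The documents do not support that as a conclusion. They speak only of potential interference, and the restriction also covers douching, lubricants and medication, which could instead suppress a positive. The upward figures above hold only under one assumed mechanism.

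The phrase clearance outside the vulva is also too wide. The cervix is sampled under the restriction at both times. For the oropharyngeal rinse, vaginal products have no evident bearing, so the point is firm for the vagina and anus and less certain for the oropharynx.

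It can fairly be said that the restriction was written for the cervical specimen, and that its reach to the swabs at follow-up is incidental. That is probably so, but following the plan exactly still produces the mismatch.

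It is also true that Week 27 and Week 48 samples are collected alike, which permits a like-for-like look at later change. Week 27 comes after the fourth dose at Week 24, however, and cannot serve as a baseline.

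Finally, the text of 6.13 and 6.16.1 in version 1.2 cannot be seen. Its change summary lists only the removal of one questionnaire and otherwise administrative edits, but that version also gained a section on the Week 38 call that the summary does not mention. Unchanged wording is therefore a reasonable assumption, not a fact. The Day 0 and follow-up schedules in version 1.2 are visible and match the table above.

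**Conclusion.** The mismatch is real. In versions 1.0 and 1.1 the restriction does not reach the Day 0 vaginal and intra-anal swabs or the oropharyngeal rinse, and it does apply at every visit where their follow-up samples are taken. Week 48 clearance at these sites may be biased, in a direction and by an amount that the protocol does not allow one to fix. The illustrative figures rest on assumed prevalence and error rates, error-free follow-up and full compliance with the request.

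The reach is small: part of one exploratory endpoint, estimated per arm without a test. Both arms follow the same schedule, so no difference between arms is implied. The primary and secondary endpoints are unaffected. This is a minor point, worth acting on because the remedy works whichever way the interference runs.

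**What to change.** In sections 6.13 and 6.16.1, extend the same 24-hour restriction to all HPV samples from outside the vulva, naming the Day 0 vaginal and intra-anal swabs and the oropharyngeal rinse as well as ThinPrep. Add a reminder to the Day 0 visit instructions in section 6.2.1. If version 1.2 already contains such wording, no change is needed.

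The cost is a sentence in each of two sections and a line in the participant instructions, with no added visit, sample or procedure. The downside is one more pre-visit request to participants. The change has to be in place before a woman's Day 0 visit, because her baseline cannot be retaken once she has been dosed.
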